A Study to Evaluate the Feasibility of Robotic
Bronchoscopy-guided Miniature Cryoprobe
Biopsy of Peripheral Pulmonary Lesions

NCT05399082

December 15, 2021

A study to evaluate the feasibility robotic bronchoscopy guided miniature cryoprobe biopsy of peripheral pulmonary lesions

Principal Investigator: [name] MD

Site(s) where study will be performed:

Mayo Clinic, Rochester, MN

1 Objectives

1.1 Primary Objective:

This is a prospective randomized control study to evaluate the feasibility of using a miniature (1.1 mm) cryoprobe to perform biopsy of peripheral pulmonary lesions using robotic bronchoscopy

1.2 Secondary Objective:

1. To assess safety of cryobiopsy through a robotic bronchoscope
2. Comparison of sample size acquired via cryobiopsy to routine forceps biopsy.
3. Comparison of quality of sample for histologic diagnosis of malignant lung lesions between cryobiopsy to routine forceps biopsy.

2 Background

Lung nodules and masses may represent primary lung cancer, metastatic disease, infection, or more benign findings such as granuloma. Often, lung nodules require biopsy to confirm a diagnosis.

Computerized tomography (CT) guided lung biopsy is the gold standard technique. Diagnostic rates are 90% or greater with excellent pathologic quality core biopsies. However, CT guided core lung biopsy is associated with a high pneumothorax rate that may be as high as 20%(1). Because of this, there has been intense interest in bronchoscopic alternatives to obtain biopsies while minimizing the risk of pneumothorax. Patients suspected of having lung cancer undergo bronchoscopy for mediastinal staging with lymph node sampling. Mayo Clinic has acquired the Ion Robot bronchoscopy system (Intuitive Surgical, Sunnyvale, CA, USA). This system uses a robotically driven 3.5 mm steerable catheter to navigate into the periphery of the lung. A 2.0 mm working channel allows the passage of needles, up to

19 gauge, and forceps to obtain biopsy specimens. Using this method, diagnostic yields are comparable to CT biopsy with a pneumothorax rate less than 2%. However, these biopsy specimens often lack adequate tissue for both diagnosis and molecular adequacy that can be obtained with CT biopsy using core needles.

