5. Histological diagnostic yield

Defined as the ability of the pathologist to make a diagnostic statement based on the histological analysis of the obtained tissue samples.

6. Total histological area (mm²)

7. Crush artifacts (% total area)

8. Fresh hemorrhage (procedural related) (% total area)

9. Other artifacts that obscure pathological assessment (% total area, artifacts will be listed)

10. Different tissue types in the tissue specimen (e.g. alveoli, bronchus, mucus, blood, target tissue; % total area) .

Safety:

11. Occurrence and grading of bleeding according to CTCAE (version 5) following each individual biopsy and overall for each procedure.

12. Occurrence and grading of the following related adverse events according to CTCAE (version 5):

a. Pneumothorax, as determine by post procedural chest x-ray, which is standard of care after robotic bronchoscopy, or any intraprocedural imaging such as cone beam CT or fluoroscopy.

b. Respiratory failure

13. Occurrence of all related adverse events Grade 3-4 (according to CTCAE) during or directly following the biopsy procedure.

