7 DSMB

The Department of Surgery DSMB will provide interim reviews and serve as in internal safety control.

8 Early Stopping Rules

If any patient is permanently disabled, has life threatening consequences (defined as Grade 3 bleeding episode or Grade 4 adverse event by CTCAE Version 5.0) the study will be temporarily halted until the DSMB has reviewed the Adverse Events. The study will be continued if the event is demonstrably unrelated to the procedure or was a reasonable adverse event in relation to the research study procedure. The trial will be permanently halted for a grade 5 event (death) if attributable to the cryobiopsy procedure. The study will be continued if the event is demonstrably unrelated to the procedure or was a reasonable adverse event in relation to the research study procedure.

9 Study Plan:

The proposed study will prospectively enroll patients being evaluated for robotic bronchoscopic lung nodule/mass biopsy which will be done as **part of their standard medical care**.

1. Patients who present for robotic navigational bronchoscopy with planned biopsy of lung nodule or mass will be eligible to consent to be included in prospective study.
2. Patients will be screened for inclusion and exclusion criteria via review of medical history and standard of care pre-procedure examinations.
3. Robotic assisted bronchoscopy will be performed as per institutional standard of care. In addition to robotic shape sensing technology, radial probe ultrasound, fluoroscopy, and cone beam CT may be used for navigation.
4. The position of the navigation catheter relative to the nodule or mass will be confirmed via radial EBUS and cone beam CT.
5. The lung nodule or mass will be biopsied using standard biopsy needles, ranging from 19-23 gauge. Rapid onsite evaluation of the needle biopsy will be performed according to standard of care.
6. Per clinical practice, after the needle biopsy we will also take tissue biopsies. We will take 3 biopsies using the 1.1 mm Erbe cryoprobe and 3 biopsies using forceps. The order in which the biopsy methods are employed will be randomized 1:1. In 50% of the patients, forceps will be

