followed by cryoprobe. In 50% of the patients cryoprobe will be followed by forceps biopsy. Randomization will take place after needle biopsy, prior to tissue biopsy. Only patients for which further tissue biopsy is deemed necessary following needle biopsy will be randomized. Remaining patients will be excluded from the study and will be treated according to the standard of care. See randomization procedure for details.

7. Cryoprobe and forceps biopsy will be performed according to standard of care and the device instructions for use. The initial freeze time for the cryobiopsy is 3 seconds as measured on the device timer. If inadequate tissue is obtained due to incomplete freeze, the freeze time can be extended by 1 second on each consecutive attempt (to a maximum of 8 seconds) at the discretion of the bronchoscopist.
8. Samples retrieved via forceps and cryoprobe biopsy will be placed into separate formalin containers and forwarded to pathology for sample processing and further pathological analysis as per standard practice.
9. Patients will be followed up for adverse events until completion of the standard of care post-procedure follow-up within 2 weeks of the procedure. The follow up may occur as a in person visit, video visit or telephone call. Adverse events will be graded using CTCAE Version 5.0 and will be attributed using the following scale:

Adverse Event Attribution Categories:

Attribution	Description
Unrelated	The AE is clearly NOT related to the intervention
Unlikely	The AE is doubtfully related to the intervention
Possible	The AE may be related to the intervention
Probable	The AE is likely related to the intervention
Definite	The AE is clearly related to the intervention

10 Randomization and Blinding

All patients will first receive needle biopsy and rapid onsite evaluation followed by tissue biopsy (forceps and cryo-biopsy). The order in which the forceps and cryo-biopsy methods are employed will be randomized 1:1. In 50% of the patients, forceps will be followed by cryoprobe. In 50% of the patients

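### Safety endpoints 12 and 13 count only 'related' events from sessions in which three devices sample one lesion; they should be all-cause, whole-session rates

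*Combined protocol and SAP*

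**What the plan says.** The first secondary objective (sections 1.2 and 5) is "To assess safety of cryobiopsy through a robotic bronchoscope". Section 6.2 gives three safety items:

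- **Item 11**, bleeding: "Occurrence and grading of bleeding according to CTCAE (version 5) following each individual biopsy and overall for each procedure". It is not limited to related events.
- **Item 12**, pneumothorax and respiratory failure: "Occurrence and grading of the following related adverse events according to CTCAE (version 5". Pneumothorax is found as follows: "Pneumothorax, as determine by post procedural chest x-ray, which is standard of care after robotic bronchoscopy, or any intraprocedural imaging".
- **Item 13**: "Occurrence of all related adverse events Grade 3-4 (according to CTCAE) during or directly following the biopsy procedure".

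Exposure is set out in sections 9 and 10. Section 9, step 5, says "The lung nodule or mass will be biopsied using standard biopsy needles, ranging from 19-23 gauge". Step 6 adds three cryoprobe and three forceps biopsies. Section 10 confirms the sequence: "All patients will first receive needle biopsy and rapid onsite evaluation followed by tissue biopsy (forceps and cryo-biopsy". Only the order of the two tissue devices is randomised, so no group goes without cryobiopsy.

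Section 9, step 9, has adverse events graded and attributed on a five-level scale from unrelated to definite, each level defined by its relation to the intervention. That term is not defined, no level is named as the cut for 'related', and no assessor is named.

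**The concern.** The objective asks about cryobiopsy, but items 12 and 13 arise in a session where three devices have entered the same lesion. A pneumothorax on the post-procedure film follows all three. Intraprocedural imaging such as cone beam CT might time an event in some patients, but none is required between devices. Whether the event is 'related' then depends on what intervention is taken to mean, and two analysts could report different counts from the same records.

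If the term is read as cryobiopsy alone, a pneumothorax judged to come from the needle or forceps drops out of item 12, and the reported figure understates what patients went through. If it is read as the whole procedure, the count is close to a session rate but could be presented as a cryobiopsy rate. Section 15.1 says the pilot is meant to inform future studies, and a DSMB safety review after 10 cases precedes phase two. The meaning of the figure therefore matters even without a formal test.

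Item 13 also stops at Grade 4, so a death would fall outside that tabulation.

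**Working it through.** **No planned figure to reproduce.** Section 15.1 gives 10 + 20 = 30 patients, with no alpha, power, margin or precision target.

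**1. Attribution terms side by side.**

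| Place | What the event is related to |
|---|---|
| 6.2, items 12 and 13 | not stated ('related') |
| 9, step 9, scale | the intervention, undefined |
| 8, continuation after review | the procedure, or the research study procedure |
| 8, permanent halt | the cryobiopsy procedure |

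Nothing in the document says that these mean the same thing.

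**2. What one decision does.** Exact (Clopper-Pearson) 95% limits for x events in n patients are the 2.5% quantile of Beta(x, n-x+1) and the 97.5% quantile of Beta(x+1, n-x). For x = 0 the upper limit is 1 - 0.025^(1/n).

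| n | x | Rate | Exact 95% CI |
|---|---|---|---|
| 30 | 0 | 0% | 0-11.6% |
| 30 | 1 | 3.3% | 0.1-17.2% |
| 30 | 2 | 6.7% | 0.8-22.1% |
| 10 (DSMB review) | 0 | 0% | 0-30.9% |
| 10 (DSMB review) | 1 | 10% | 0.3-44.5% |

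**3. How likely a disputed event is.** Section 2 puts pneumothorax with robotic needle and forceps biopsy below 2%. Taking 2% as an upper value, and assuming that cryobiopsy adds nothing:

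- expected events = 30 × 0.02 = 0.6;
- P(at least one) = 1 - 0.98^30 = 45.5%.

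At an assumed 1%, the figures are 0.3 events and 1 - 0.99^30 = 26.0%.

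**4. How far the 'related' rate can move.** Let b be the needle and forceps background and c an assumed cryobiopsy increment, acting independently. The session rate is 1 - (1-b)(1-c). The 'related' rate lies between c (no background event called related) and the session rate (all called related). With b = 2%:

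| c (assumed) | Session rate | Range of 'related' rate |
|---|---|---|
| 0% | 2.0% | 0-2.0% |
| 2% | 4.0% | 2.0-4.0% |
| 5% | 6.9% | 5.0-6.9% |

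The spread is b(1-c), at most 2 points. That is small against an interval of 0-11.6% for 0/30, so the problem is what the figure means rather than its precision.

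**5. Item 11.** Bleeding is not filtered by relatedness and is graded "following each individual biopsy and overall for each procedure". Biopsy-level data by device and a session figure are therefore both already planned.

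**The case against.** The strongest reply is that this is an unpowered, descriptive pilot with safety as a secondary objective. Adverse events are attributed on all five levels, including unrelated, so all-cause events appear to be collected and could be listed anyway. If intervention means the whole procedure, a needle pneumothorax already counts as related and nothing is lost. Dropping the filter also moves the figure further from a cryobiopsy rate. All of this stands as a limit on severity. It does not remove the gap: the document does not settle the meaning, and items 12 and 13 as written report related events only. The all-cause figure is no cryobiopsy rate either, but if labelled as a session rate it says what it measures.

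A reader might infer three stronger points, which the document does not support:

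- **That attribution is unblinded.** Section 10 says the bronchoscopist is unblinded once the order is revealed, but no one is named as attributing events. Blinding would not separate three devices used in every patient in any case.
- **That the bleeding endpoint shares the defect.** It has no 'related' filter.
- **That bleeding carried over from the first device dilutes a cryoprobe-forceps comparison, so the first-device contrast should be the main analysis.** No pooled bleeding contrast is planned; only the objectives on sample size and quality are comparisons. The change would also be a trade-off. Assume first-device bleeding of 30% (cryoprobe) and 10% (forceps), 15 patients per order, and a 60% chance that a patient who bled after the first device is graded as bleeding after the second. The first-device contrast has SE = √((0.3×0.7 + 0.1×0.9)/15) = 0.141. The pooled within-patient contrast has SE about 0.086 and bias 0.20 - 0.14 = 0.06, so its root mean squared error is √(0.086² + 0.06²), about 0.105. Needle bleeding can also carry into the first-device grade.

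**Conclusion.** The point holds for items 12 and 13 and is minor. As written, they report a judgement with no stated referent, cut or assessor, on events that generally cannot be assigned to one device. One decision moves the final rate between 0% and 3.3% at n = 30, and the rate at the DSMB review between 0% and 10% at n = 10. Understatement is possible, not shown: it depends on intervention being read as cryobiopsy alone. At the document's upper background of 2%, filtering can shift the underlying rate by at most about 2 points, well inside the sampling uncertainty. The cryobiopsy increments and the independence of the two sources are assumptions; the 2% is the upper bound in section 2. The omission of grade 5 from item 13 rests on the wording alone.

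**What to change.** - In items 12 and 13, count all pneumothorax, all respiratory failure and all grade 3 or higher events, including grade 5, regardless of attribution. Keep each item's existing time window, and list the five-level attribution beside each event.
- Label these figures as whole-session rates (needle + forceps + cryoprobe), not cryobiopsy rates, and give exact 95% intervals.
- Define the intervention in the section 9 scale, say which levels count as 'related', and name the assessor by role. The attribution terms in sections 8 and 9 must be reconciled; which of them should govern study conduct is for the sponsor and the DSMB.
- Leave item 11 as it is. Its per-biopsy bleeding grades can be tabulated by device and by order, descriptively.

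The cost is a change of wording and one listing. The plan already has adverse events recorded, graded and attributed, so no new procedure, patient or data item is needed. The downside is that the all-cause rate may be slightly higher and includes needle and forceps background, which the label must make plain.

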7 DSMB

The Department of Surgery DSMB will provide interim reviews and serve as in internal safety control.

8 Early Stopping Rules

If any patient is permanently disabled, has life threatening consequences (defined as Grade 3 bleeding episode or Grade 4 adverse event by CTCAE Version 5.0) the study will be temporarily halted until the DSMB has reviewed the Adverse Events. The study will be continued if the event is demonstrably unrelated to the procedure or was a reasonable adverse event in relation to the research study procedure. The trial will be permanently halted for a grade 5 event (death) if attributable to the cryobiopsy procedure. The study will be continued if the event is demonstrably unrelated to the procedure or was a reasonable adverse event in relation to the research study procedure.

9 Study Plan:

The proposed study will prospectively enroll patients being evaluated for robotic bronchoscopic lung nodule/mass biopsy which will be done as **part of their standard medical care**.

1. Patients who present for robotic navigational bronchoscopy with planned biopsy of lung nodule or mass will be eligible to consent to be included in prospective study.
2. Patients will be screened for inclusion and exclusion criteria via review of medical history and standard of care pre-procedure examinations.
3. Robotic assisted bronchoscopy will be performed as per institutional standard of care. In addition to robotic shape sensing technology, radial probe ultrasound, fluoroscopy, and cone beam CT may be used for navigation.
4. The position of the navigation catheter relative to the nodule or mass will be confirmed via radial EBUS and cone beam CT.
5. The lung nodule or mass will be biopsied using standard biopsy needles, ranging from 19-23 gauge. Rapid onsite evaluation of the needle biopsy will be performed according to standard of care.
6. Per clinical practice, after the needle biopsy we will also take tissue biopsies. We will take 3 biopsies using the 1.1 mm Erbe cryoprobe and 3 biopsies using forceps. The order in which the biopsy methods are employed will be randomized 1:1. In 50% of the patients, forceps will be

followed by cryoprobe. In 50% of the patients cryoprobe will be followed by forceps biopsy. Randomization will take place after needle biopsy, prior to tissue biopsy. Only patients for which further tissue biopsy is deemed necessary following needle biopsy will be randomized. Remaining patients will be excluded from the study and will be treated according to the standard of care. See randomization procedure for details.

7. Cryoprobe and forceps biopsy will be performed according to standard of care and the device instructions for use. The initial freeze time for the cryobiopsy is 3 seconds as measured on the device timer. If inadequate tissue is obtained due to incomplete freeze, the freeze time can be extended by 1 second on each consecutive attempt (to a maximum of 8 seconds) at the discretion of the bronchoscopist.
8. Samples retrieved via forceps and cryoprobe biopsy will be placed into separate formalin containers and forwarded to pathology for sample processing and further pathological analysis as per standard practice.
9. Patients will be followed up for adverse events until completion of the standard of care post-procedure follow-up within 2 weeks of the procedure. The follow up may occur as a in person visit, video visit or telephone call. Adverse events will be graded using CTCAE Version 5.0 and will be attributed using the following scale:

Adverse Event Attribution Categories:

Attribution	Description
Unrelated	The AE is clearly NOT related to the intervention
Unlikely	The AE is doubtfully related to the intervention
Possible	The AE may be related to the intervention
Probable	The AE is likely related to the intervention
Definite	The AE is clearly related to the intervention

10 Randomization and Blinding

All patients will first receive needle biopsy and rapid onsite evaluation followed by tissue biopsy (forceps and cryo-biopsy). The order in which the forceps and cryo-biopsy methods are employed will be randomized 1:1. In 50% of the patients, forceps will be followed by cryoprobe. In 50% of the patients

cryoprobe will be followed by forceps biopsy. Randomization will take place inter-procedurally; after needle biopsy and prior to tissue biopsy. Only patients for whom, in the opinion of the investigator, further tissue biopsy is medically advisable, will be randomized. Remaining patients will be excluded from the study and will be treated according to the standard of care. See Figure 1 for the randomization schema.

Sealed envelopes will be prepared at the beginning of the study using an independently managed (a research professional that is not a member of the study team) double-blinded envelope system. The double-blinded envelope will be opened at the randomization timepoint (intra-procedurally after needle biopsy and just prior to the tissue-biopsy) to reveal the order of methods (forceps/cryobiopsy). If a further biopsy is not deemed necessary or medically advisable, the patient will be excluded from the study. The unopened randomization envelope will be replaced, and will be used for the next eligible participant.

Allocation will be double blinded to patient and bronchoscopist until the intra-procedural randomization timepoint after which blinding of the bronchoscopist is not possible due to the nature of the procedure. Pathologists interpreting the biopsy samples will be blinded to the biopsy device used although, due to the expected differences in biopsy size and appearance, the allocation of the biopsy method may be apparent. Unblinding will be performed in case of medical need or if required by regulatory or legal authorities.

11 Devices and Equipment

The following devices will be used to perform the transbronchial biopsy procedure.

- Intuitive Ion Robot platform (Sunnyvale, CA)
- Bronchoscope: Olympus P190 bronchoscope (Olympus, USA).
- Biopsy Needle: 23-gauge Flexision Biopsy Needle (Intuitive, USA)
- Biopsy forceps: Olympus disposable EndoJaw (FB-211), Olympus, USA)
- Cryoprobe: Flexible cryoprobe, single-use, Ø 1.1 mm (Erbe Elektromedizin GmbH, 20402-401) used with ERBECRYO 2 (Erbe Elektromedizin GmbH, 10402-000)
- Radial probe ultrasound: (Olympus, USA)
- Cone beam CT and fluoroscopy (Cios C-spin, Siemens)

All other procedural devices and equipment will be used according to institutional availability and standard of care.

12 Schedule of Events

	Screening max. 30d prior to procedure	Procedure	Follow Up
Informed consent	X		
Review of inclusion and exclusion criteria	X	X	
Medical chart review and medical history	X		X
Review concomitant medication	X	X	
Clinical assessment/physical exam	X	X	
Urine pregnancy test (for women of child bearing potential as standard of care)	X**	X**	
Robotic-assisted bronchoscopy procedure		X	
Randomization		X	
Follow-up Chest X-ray		X*	
Adverse events	X	X	X***

*Post-procedure standard of care x-ray is done prior to discharge.

** Standard of care pre-procedure pregnancy test, on the day of the procedure if not done 30-days prior.

*** In person, video, or telephone

13 Specimen processing

For specimen processing, cryobiopsy and forceps specimens will be placed in separate formalin containers and evaluated by a dedicated pulmonary pathologist.

14 Data Collection and Confidentiality Procedures:

The following data will be collected from the patient's medical record:

1. Demographic data (such as age, gender, BMI, and other non-identifiable demographics)
2. Past medical history
3. Nodule characteristic (size, location, presence of bronchus sign, PET avidity, central lucency, distance to the pleural surface, distance to the nearest visible bronchus)
4. History of prior treatments
5. Indication for procedure
6. Radiologic data
7. Preliminary ROSE assessment (Rapid On-Site Evaluation) and final histopathology result

The following technical procedural data will be collected:

1. Position of the robotic catheter relative to the nodule prior to biopsy sampling as assessed via rEBUS ("concentric", "eccentric" or "adjacent" orientation) and/or cone beam CT.
2. Procedural details such as number of biopsies performed, duration of procedure, freezing time for cryoprobe

Study data will be collected and managed using REDCap (Research Electronic Data Capture). REDCap (www.project-redcap.org) is a secure, web-based application, with controlled access designed to support data capture for research studies. It provides: 1) an intuitive interface for validated data entry; 2) audit trails for tracking data manipulation and export procedures; 3) automated export procedures for seamless downloads to common statistical packages; and 4) procedures for importing data from external sources.

Access to the data will include the study PI and research team personnel. All protected health information (PHI) will be removed from the data when it is exported from REDCap for analysis.

Study data will be archived indefinitely in REDCap following publication. This will allow the data to be used in future research studies performed under separate IRB approved protocols. REDCap is a secure electronic database with controlled access, and because patient identifiers may be needed to link study data to data from other sources under future IRB approved protocols, thus patient identifying information will be retained in the archived database.

15 Statistical analysis

All statistical analyses will be performed in collaboration with the Mayo Clinic Department of Biostatistics.

A descriptive analysis will be done first. Descriptive statistics (e.g., frequencies, ranges, means, medians, proportions, and standard deviations [SDs]) along with 95% confidence intervals (CIs) for the means or proportions will be computed for the measures of interest described in primary and secondary objectives.

[figure not shown]

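### Section 8 repeats its continuation sentence straight after the permanent-halt rule for death; as written, one limb of it contradicts that rule

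*Combined protocol and SAP*

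**What the plan says.** Section 8 of the combined protocol and SAP has four sentences.

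1. A temporary halt pending DSMB review if a patient is permanently disabled or "has life threatening consequences (defined as Grade 3 bleeding episode or Grade 4 adverse event by CTCAE Version 5.0").
2. A continuation sentence with two alternative grounds: the event is shown to be unrelated to the procedure, or it falls under the limb "or was a reasonable adverse event in relation to the research study procedure".
3. The permanent-halt rule: "The trial will be permanently halted for a grade 5 event (death) if attributable to the cryobiopsy procedure".
4. Sentence 2 again, identical in wording.

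The join between sentences 3 and 4 reads: "if attributable to the cryobiopsy procedure. The study will be continued if the event is demonstrably unrelated to the procedure or was a reasonable", and then runs on to the end of the second ground.

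Two other places bear on the DSMB. Section 7 gives it interim reviews and an internal safety role. Section 15.1 schedules a safety review after the first 10 of 30 patients, with progression if the risk is found acceptable.

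**The concern.** Sentence 3 is mandatory and carries no exception. Sentence 4 follows at once, and the event it speaks of is most naturally the death just named. Its second ground for continuing is an event that counts as reasonable in relation to the research procedure. The documents do not say what that means for a stopping decision or who decides it. Read literally, the text offers a route to continue after a death attributable to cryobiopsy, which is the outcome sentence 3 rules out.

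At stake is the clarity of the study's strictest safety rule. It would be applied soon after a death, in a study of a technique that Section 2 says has not previously been combined with robotic bronchoscopy. Nobody should then have to argue over which of two adjacent sentences governs.

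**Working it through.** The point concerns wording, so there is no figure to reproduce. The check compares the sentences and then takes each kind of death in turn.

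**Comparison.** Sentences 2 and 4 are identical. Sentence 2 fits its place: after a temporary halt and DSMB review, it says when the study resumes. Sentence 4 follows a permanent halt, after which there is nothing to resume.

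**Cases under the present text.**

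| Death | Sentence 3 | Sentence 4 | Result |
|---|---|---|---|
| A. Shown to be unrelated | not triggered | continue | consistent |
| B. Attributable to cryobiopsy, not judged reasonable | halt permanently | silent | consistent |
| C. Attributable to cryobiopsy, judged reasonable | halt permanently | continue | **contradiction** |
| D. Not attributable to cryobiopsy, not shown to be unrelated, judged reasonable | not triggered | continue | no conflict |
| E. As D, but not judged reasonable | not triggered | silent | no conflict, but no instruction here |

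The conflict arises in case C alone, and only through the limb "or was a reasonable adverse event in relation to the research study procedure".

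**Does anything else settle case C?** Section 7 gives the DSMB a general role without ranking the two sentences. The review in Section 15.1 falls after 10 cases and does not govern a death. Neither defines the reasonable-event ground.

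**Would deleting sentence 4 be enough?** Deletion removes the contradiction in C. It also leaves A, D and E with no stated action, because the trigger in sentence 1 names permanent disability, Grade 3 bleeding and Grade 4 events but not Grade 5. Cases D and E are conceivable because every randomized patient has three kinds of biopsy in one session: "All patients will first receive needle biopsy and rapid onsite evaluation followed by tissue biopsy", and then "We will take 3 biopsies using the 1.1 mm Erbe cryoprobe and 3 biopsies using forceps". A death might therefore be put down to the needle or forceps, or be hard to assign to one device. Replacing the sentence is better than deleting it.

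**The case against.** The best defence is that nobody would be misled. The repetition looks like a copying slip, and a specific mandatory rule would normally prevail over a repeated general one. Sentence 4 can also be read as covering only deaths that sentence 3 does not reach. Much of this stands: the intent is apparent and a careful reader would probably halt the trial, which is why the point is minor. It does not remove the defect. The text does not confine sentence 4 to other deaths, and if only unrelated deaths were meant, the second limb has no purpose there.

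A reader might infer more than the documents support.

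- *That the plan as it stands has no rule for deaths from needle or forceps biopsy, or of uncertain cause.* Sentence 4 does address them: it allows continuation if they are unrelated or reasonable. The gap opens mainly once that sentence is deleted. A fatal complication that was first life-threatening could also have met the Grade 4 trigger in sentence 1.
- *That deaths go uncaptured because one safety endpoint covers "Occurrence of all related adverse events Grade 3-4 (according to CTCAE) during or directly following the biopsy procedure".* That is an endpoint definition, not a stopping rule. Endpoints 11 and 12 in Section 6.2 grade bleeding, pneumothorax and respiratory failure by CTCAE with no upper limit.
- *That the rule fails because the word attributable is not tied to the five-level scale in Section 9, item 9* ("Adverse events will be graded using CTCAE Version 5.0 and will be attributed using the following scale"). Section 8 does not invoke that scale. Choosing a cut-off is added detail with a real trade-off: if Possible counted, a death that merely may be related would end the trial automatically. The contradiction exists wherever the cut-off is set.

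**Conclusion.** The point holds: Section 8 is wrong as written, with minor severity. One of the five cases above carries two opposite instructions, and nothing else in the documents resolves them. The conclusion assumes that the event in sentence 4 is the death named in sentence 3, which is the natural reading. That the repetition is a slip is an inference from its identical wording and poor fit, and the conclusion does not depend on it. The documents give no expected frequency of a cryobiopsy-attributable death, so none is estimated. They do not support a claim that the sponsor intends to continue after such a death, or that the feasibility endpoint, the sample of 30, the randomization or the analysis is affected.

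**What to change.** Keep sentences 1 to 3 of Section 8. Replace the second continuation sentence with:

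> Any other death will temporarily halt the study until the DSMB has reviewed it; the study will be continued without further action only if the death is demonstrably unrelated to the study procedures, and otherwise only if the DSMB judges it safe to continue.

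Each case then has one course of action. A cryobiopsy-attributable death (B, C) ends the trial. An unrelated death (A) leads to review and resumption. Any remaining death (D, E), including one caused by needle or forceps, leads to review and a DSMB decision, with no obligation to continue. Sentence 2 stays, because after DSMB review of the events in sentence 1 it contradicts nothing.

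The cost is one replaced sentence and a possible pause for DSMB review after a death not attributed to cryobiopsy. No endpoint, sample size or analysis changes.
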